The child facing a parent's cancer: a randomized study evaluating the effectiveness of a psychological intervention designed to support parenting.

Protocol

Unique Protocol ID:

Bordet CE2681

Erasme SRB 201805 132.

20/12/2018

[name] (ULB)

[name] (ULB-IJB)

[name] (IJB)

1. Introduction.

In Belgium, more than 74,000 new cancers were diagnosed in 2014[1]. In the United States, it is estimated that 18% of adults diagnosed with cancer and 14% of patients in remission have dependent children under 18 years of age[2]. When faced with their parent's cancer, children experience more negative emotions (e.g., guilt, anger, sadness) as well as disease-specific fears (e.g., fear of uncertainty, fear of losing their parent)[3]. According to the literature, they are at greater risk of developing psycho-emotional difficulties (i.e., stress, anxiety, depression)[3-5] and of using mental health services more often in both childhood and adulthood[6]. The parental cancer experience has therefore an impact on children in the short, medium and long term. Maintaining a safe environment favorable to child development is likely to limit the impact of cancer[7]. The international group "Children of Somatically Ill Parents" (COSIP)[8] has also made recommendations to this effect.

Following a cancer diagnosis, nearly 10 to 50% of patients report high levels of psychological and emotional distress[9], which is comparable to those reported by their relatives[10, 11]. When patients and relatives are parents, they report specific concerns about the impact of the disease on their child and the support they need to provide[12]. Some parents are afraid to discuss the illness with their child, fearing to add additional distress to them[13]. Regardless of effective parenting skills, the distress of parents (sick or not) has also an impact on the feeling of parenting skills[14, 15]. As a result, some parents no longer feel able to meet their child's needs. This decrease in the sense of parental competence could be associated with difficulties in implementing some supportive behaviours such as communication and with difficulties in emotional regulation in this context. In addition, some parents report a lack of knowledge about supporting a child with a parent's cancer and therefore do not know how to approach cancer with their child[12]. Cancer therefore implies for sick and non sick parents, in addition to managing the physical and psychological impact of diagnosis and treatment, the development of new parental behaviours to be jointly implemented.

To meet these specific needs, many recommendations are made for parents, including brochures. Several interventions have also been created in various ways[16, 17]. Some interventions are specifically addressed to parents, others to children and some others to the whole family. Most oncology intervention studies around child or family support are qualitative studies that do not meet the scientific research criteria as described by "CONSORT"[18]. Nevertheless, despite the heterogeneity of the interventions and the quality

of the designs evaluating the interventions, the literature shows that they have a positive overall impact[16].

There are currently only a few randomized studies evaluating the effectiveness of a psychological intervention to support parenthood that focuses on helping the child in an oncological context and that is offered to significant caregiver of the child. As part of a randomized and controlled study, a psychological intervention to support parenting was developed at the Jules Bordet Institute. This intervention is offered to significant caregivers of a child who have questions about the support a child needs when confronted with a parent's cancer. This intervention aims to develop and reinforce these supportive behaviors. The intervention is intended to be flexible (to respond to the medical situation), relatively brief (four sessions) and open to the heterogeneity of families (e.g., reconstituted, divorced, extended family). Significant caregiver of the child can participate either in pairs (in dyads) or individually.

2. Objectives of the study.

The intervention is evaluated in a randomized controlled study. To do this, two conditions are compared. The first condition ("control" condition) consists in the delivery of an information booklet entitled "How to talk with the child about a parental cancer? A practical booklet on communication. "[23] which contains parental information and recommendations associated with supporting a child facing a parent's cancer. The second condition ("experimental" condition) consists, in addition to providing the same information booklet, of a psychological intervention focused on supporting the child who has a parent with cancer.

2.1. Primary Objective.

The main objective of this study is to test the contribution and effectiveness of a psychological intervention in relation to the delivery of an informational booklet regarding participants' communication with the child in the oncology context. This intervention should increase participants' sense of communicative competence and communication behaviors.

2.2. Secondary objectives.

The information booklet should more specifically improve participants' knowledge of how to support a child facing a parent's cancer. Psychological intervention should have an impact not only on the sense of communicative skills but also on the emotional regulating capacity

associated with participants' communication with the child and on participants' concerns about the child. When the intervention is carried out in a dyad, it should also improve mutual support between participants.

3. Method

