parental competence (Moore, 2015). In this way, a more systematic recruitment will be organised within the Jules Bordet Institute at the day hospital and in radiotherapy in agreement with the department heads. In addition, in order to facilitate families' access to the project, the study is being disseminated to front-line carers (doctors, nurses, psychologists, social workers, NOC, etc.) within the Jules Bordet Institute, Erasmus Hospital and also in other hospitals via the distribution of information sheets and oral presentations.

3.2. Description of the study.

This is a randomized longitudinal controlled study conducted at the Jules Bordet Institute site and at Erasmus Hospital (Figure 1). This study evaluates the effectiveness of a psychological intervention focused on helping children in the oncology context. Significant caregivers may participate alone or in dyads at the intervention. At the time of recruitment (T0), after checking the eligibility criteria, participants receive all the information associated with the study. As a first step, they are offered the opportunity to perform the dyad intervention. If this is not possible, participants have the opportunity to participate in an individual way. After this step of presenting the information, they sign a consent form for inclusion in the study. As soon as they are included, the participants (in dyads or individually) have a first evaluation time (T1) consisting of the completion of questionnaires and a semi-directive interview.

[figure not shown]
At the end of T1, all participants (experimental condition and control condition) receive an information booklet entitled "How to talk with the child about a parental cancer? A practical booklet on communication. "[23] which contains parental information and recommendations associated with supporting a child facing a parent's cancer.

After T1, each participant is directly randomly assigned to either the experimental or control condition. Randomization is done after the first evaluation so that evaluators and participants are not aware of the distribution at T1.

After receiving the information booklet, participants randomized to the experimental condition receive a brief parental support intervention consisting of four sessions. Fifteen days after the end of the intervention, these participants have a second evaluation (T2), again consisting of the completion of questionnaires and a semi-directive interview.

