After receiving the information booklet, randomized participants in the control condition are placed on a waiting list. Nine weeks after the end of T1, these participants have a second evaluation time (T2) consisting of the completion of questionnaires and a semi-directive interview. They subsequently benefit from parental support intervention.

The entire study was manualized and standardized in order to best meet the methodological recommendations recommended by "CONSORT"[18].

Information booklet: "How to talk to your child about a parental cancer? A practical booklet on communication. » [23]

All participants (control and experimental conditions) receive an information booklet containing parental information and recommendations associated with supporting a child facing a parent's cancer. To address this theme, the booklet describes concepts related to child

development such as understanding the disease, reactions and needs. It also presents recommendations related to communication around the disease according to the child's age and development (*what to say to the child?* and *how to respond to the child?*). Finally, the booklet offers resources (e.g., books, websites, non-profit organisations) that are useful in this context.

3.3. Parental Support Intervention.

3.3.1. Objectives of the intervention.

While the information booklet mainly aims to increase the knowledge of significant caregivers about supporting a child facing a parent's cancer, the parental support intervention aims to develop and reinforce their behaviors associated with supporting the child in this context. The intervention aims to improve communication with the child by strengthening the sense of communicative competence and transmitting emotional regulation strategies. The dyad intervention also aims to strengthen mutual support between participants.

3.3.2. Content of the intervention.

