This is a brief four-session parental support psychological intervention that can be done individually or in a dyad. The first session is dedicated to a global assessment of the medical and family situation, communication with the child, as well as to an identification and reinforcement of the participant's parental skills. The second session suggests to the participant to identify the reactions and needs of children in the context of the disease and based on concrete examples. A construction work of what can influence perception is carried out. The last two sessions are devoted to the participant's specific questions about communicating with his or her children in the context of the disease.

In general, emotional regulation techniques specific to parenthood are worked on during the session and reinforced by the transmission of a relaxation booklet. Parental competence is systematically supported and strengthened. The content does not change whether one is in a dyadic or individual intervention except that dyadic interactions and support are enhanced.

Our workers are trained in the management of families through their clinical practice within the activities of "Bordet'N Family". In order to increase the fidelity of intervention replication, future practitioners will also benefit from a training process that involves three stages: general theoretical training in intervention, practical training specific to the intervention and

supervisions scheduled after each session with an experienced psychologist. In addition, the workers are supervised by the study coordinator ([name]).

A quality control of the intervention is set up by an audio and video recording of the interventions. These records are regularly analyzed using an analysis grid created from the intervention manual to verify the standardization of the intervention.

3.4. Evaluation procedure and questionnaires.

This study includes 2 evaluation periods, T1 and T2, consisting of the completion of questionnaires and a semi-directive individual interview. The evaluation procedure includes a research interview which is structured in three parts. The entire research interview lasts approximately 1h30.

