The first part focuses on supporting the child facing a parent's cancer. To do this, participants are asked to complete several questionnaires with specific reference to only one child in their circle. This child must face a parent's cancer and must be between 3 and 18 years old. If several children meet these criteria, the participant determines the one for whom he or she has the most questions about how to communicate with him or her about the disease. When it comes to dyads, participants agree on the choice of the child. The child identified serves as a reference during both T1 and T2 in order to standardize the assessment procedure as much as possible. Participants are invited to complete questionnaires describing the situation of the identified child, as well as questionnaires focusing on their parental concern and support for the child.

- Individual intervention:
 - The socio-demographic data of the identified child.
 - The relationship of the participant(s) to the identified child.
 - The medical context of the disease. Two versions of this questionnaire were created for the study: one for non-patient participants and one for sick participants.
 - The sense of communicative competence. A questionnaire developed specifically for the study was created from the theories of parental competence in oncology and self-efficacy theories[13-15, 19].
 - Communication with the child. The participant's communication with the child is assessed by a questionnaire specifically developed for the study. This questionnaire contains two

subscales: communication with the child and the emotional regulation associated with this communication.

- Concerns about the identified child. An adaptation of Muriel et al.'s Parenting Concerns Questionnaire (PCQ)[2] was developed for the study. Since the PCQ is an oncology patient questionnaire, one item has been removed so that all items can be adapted to all participants.
- The feeling of knowledge. The participants' sense of knowledge about the support to the identified child is assessed by a questionnaire specifically developed for the study. This questionnaire was created from the concepts developed in the information booklet.

- Dyad intervention:

- idem plus two questionnaires, the first evaluating the relationship with the person who supports them in relation to the child and the second evaluating the mutual support between the participants by means of a questionnaire specifically developed for the study.

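### Section 2.2 makes a booklet effect on knowledge a secondary objective, but both arms get the same booklet, so only an uncontrolled T1-T2 change can address it

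*Protocol*

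**What the plan says.** Protocol section 2.2 (Secondary objectives) opens with: "The information booklet should more specifically improve participants' knowledge of how to support a child facing a parent's cancer". The expected effects of the psychological intervention follow in the same section. Section 3.3.1 repeats the division of labour: the booklet is mainly aimed at knowledge, the sessions at supportive behaviours.

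The control condition in section 2 is the booklet. The other arm is described there as follows: "in addition to providing the same information booklet, of a psychological intervention focused on supporting the child who has a parent with cancer". Section 3.2 fixes the timing: "At the end of T1, all participants (experimental condition and control condition) receive an information booklet". Controls are then on a waiting list, are reassessed nine weeks after the end of T1, and receive the sessions only after that. Experimental participants are reassessed fifteen days after the sessions end.

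Section 3.4 states: "This study includes 2 evaluation periods, T1 and T2". Two questionnaires concern knowledge. One covers the feeling of knowledge about supporting the child, and of it the protocol says "This questionnaire was created from the concepts developed in the information booklet". The other covers knowledge of how children understand the disease. Section 3.4 also records booklet use and relevance at T2. The only efficacy model in section 3.5 compares change between the two arms in order to test the intervention.

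**The concern.** The objective has the booklet as its subject, a causal verb and no descriptive label, and it stands among the objectives of a randomised trial. To show that the booklet improves knowledge, the trial would need participants without the booklet, or some other way to separate its effect from everything else that happens between T1 and T2. It has neither.

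What is at stake is one conclusion. If knowledge rises in the control arm, or in both arms, the objective as worded invites a report that the booklet has been shown to work. The reader would take that as a finding of a randomised study, although the randomisation contributes nothing to it. This goes beyond what an SAP can settle. An SAP can choose an estimator and a label, but the arms and assessment times are set in the protocol, and they leave no controlled estimate of the booklet effect.

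**Working it through.** **The plan's own figure.** Section 3.1 asks for 34 per group (68 in total) for an effect size of 0.8, 5% significance and 90% power. A two-sided two-sample t-test gives 33.83, so 34 per arm, with power 0.9015. Recruiting 80 corresponds to 15% dropout (68/0.85 = 80). These figures reproduce and are not in dispute. They concern the comparison between arms.

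**What each comparison estimates.** Let b be the booklet effect on knowledge, s what the sessions add, and d_C and d_E the change from time, retesting and other care in the control and experimental arms.

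- Control change, T1 to T2: b + d_C
- Experimental change, T1 to T2: b + s + d_E
- Arm contrast: (b + s + d_E) − (b + d_C) = s + (d_E − d_C)

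The common b drops out of the contrast whatever its size. T2 is timed differently in the two arms, so d_E and d_C need not be equal. That affects how s is read, but it does not bring b back.

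**Can the experimental arm's change stand for the booklet?** Not safely. Section 3.2 says the booklet covers aspects of child "development such as understanding the disease, reactions and needs". Section 3.3.2 says: "The second session suggests to the participant to identify the reactions and needs of children in the context of the disease". Both components touch the same topic, so this arm's change may mix b and s. The protocol does not document how far they overlap.

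**Can the control arm's change?** It is free of the sessions but equals b + d_C. The interval is nine weeks, the questionnaires are repeated, and section 4 allows ordinary psychosocial care during the study. With one assessment before the booklet and one after it, b and d_C cannot be told apart.

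**Can recorded booklet use help?** Use was not randomised. Participants who use the booklet more may differ in motivation or in initial knowledge, so relating use to knowledge gives no controlled estimate.

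**Illustration by simulation.** Assumptions: 34 per arm, SD of the change set to 1, independent participants, s = 0. The values of b and d_C are chosen for illustration, since the protocol gives none.

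| Test | True state | Share of runs significant |
|---|---|---|
| Arm contrast | b = 0 | 5.0% |
| Arm contrast | b = 0.5 | 4.5% |
| Arm contrast | b = 1.0 | 4.7% |
| Control change | b = 0.5, d_C = 0 | about 81% |
| Control change | b = 0, d_C = 0.5 | about 81% |
| Control change | b = 0, d_C = 0.2 | about 20% |

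The contrast stays near 5% whatever b is. The control-arm test responds equally to the booklet and to drift of the same size.

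**Illustrative precision**, in SDs of the T1-T2 change:

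- Control-arm change, n = 34: t(0.975; 33)/√34 = 0.349, about 0.35
- Arm contrast, 34 per arm: t(0.975; 66) × √(2/34) = 0.484, about 0.48

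Section 3.5 analyses individual and dyad participants separately, so the working half-widths are larger. With an assumed even split of 17 per arm in each stratum they become t(0.975; 16)/√17 = 0.51 and t(0.975; 32) × √(2/17) = 0.70. Positive correlation within dyads would widen the control-arm interval further.

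**The case against.** The best defence is that the sentence is rationale. It says what should happen, and it contrasts the booklet's target with the sessions' targets named in the next sentence, as section 3.3.1 does again. Read that way, it says only which component is expected to act on which outcome, and T1-T2 data can describe the expected pattern of a rise in both arms. Section 2 says that it is the intervention that is evaluated, and section 3.5 plans no test of the booklet. A before-after secondary objective is legitimate, and its labelling could be left to an SAP.

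Much of this stands. A reader might infer that the protocol intends the randomised comparison to test the booklet. It does not say so, and section 3.5 points the other way. What does not stand is that the sentence can therefore remain as it is. It is listed as an objective, so it will be reported against, and its wording asks for a causal answer.

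Two other stronger readings also fail. One is that the sessions repeat the booklet's content: the evidence is one shared topic, and session 2 works from concrete examples while the last two sessions take up the participant's own questions. The other is that a bias can be put in numbers by pooling the arms and applying the 0.8 planning effect to knowledge: the protocol plans no pooled analysis and does not tie 0.8 to knowledge.

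**Conclusion.** The point holds as a minor one. The secondary objective about the booklet cannot be answered by the randomised comparison. The only change free of the sessions is the control arm's, and it is uncontrolled. This follows from the arms and assessment times alone and needs no numerical assumption, beyond taking the booklet effect as common to both arms, who receive the same booklet at the same point.

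The size of a possible misattribution is unknown, because the documents give no value for the booklet effect, the drift or the SD of the change. The half-widths of 0.35 and 0.48 SD are illustrations for all 34 per arm with independent participants, and both are wider under the separate individual and dyad analyses.

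A reader might infer that the trial's main result is weakened. It is not. The primary objective compares the intervention plus booklet with the booklet alone, and the sample size serves that comparison.

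**What to change.** Replace the first sentence of section 2.2 with a descriptive objective, for example: *to describe the T1-T2 change in the control arm on the two knowledge questionnaires (feeling of knowledge; knowledge of children's understanding of the disease), with 95% confidence intervals; this change is uncontrolled and is not attributed causally to the booklet.*

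Optionally, add the question on knowledge that the randomisation can address: whether the intervention plus booklet changes knowledge more than the booklet alone, estimated as the arm-by-time contrast. The investigators have not stated this hypothesis, so it should be labelled as an added secondary question. If booklet use is related to knowledge, that analysis should be labelled non-randomised.

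The cost is one reworded sentence and one descriptive estimate from questionnaires already completed at both times. The real price is giving up a causal claim for the booklet, which the design could not have supported. The optional contrast adds one secondary hypothesis. The primary objective, arms, visits and sample size stay as they are.
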